2.3 Exploratory purpose

- To explore the possible effects of PD-L1 expression on efficacy.
- To explore molecular biology markers that can predict efficacy.

3. Study Design

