3.1. Overall design

This is a prospective, single-arm, open-label phase II clinical trial in which IBI308 intravenous chemotherapy is combined with oral administration of anlotinib for recurrent or advanced endometrial cancer. The primary objective is to assess the ORR of IBI308 intravenous chemotherapy combined with anlotinib for recurrent or advanced endometrial cancer in patients who failed first-line chemotherapy based on the irRECIST and RECIST 1.1 criteria. Subjects will receive IBI308 200 mg intravenously q3w and anlotinib 12 mg qd d1–

d14 q3w po until a protocol-stipulated treatment termination event occurs. Subject visits will continue after treatment has ended.

Evaluation is performed once after the 2nd treatment cycle (C3) and once after the 4th treatment cycle (C5) since the first dose. Subsequently, an evaluation will be performed once after the 7th treatment cycle (C8) and once after the 10th treatment cycle (C11). After the 10th cycle, an evaluation will be performed once every 4 treatment cycles, and the time window for radiologic evaluation is ± 7 days.

Simon's 2-stage design was used for sample size estimation, with an alpha of 0.05 (one-tailed) and a beta of 0.2 (power of 0.8). Based on existing literature, the ORR of anti-PD-1 monoclonal antibody monotherapy for advanced or recurrent PD-L1-positive endometrial carcinoma in patients who failed first-line chemotherapy is 13%. Assuming that a combination of IBI308 and anlotinib can increase efficacy by 26%, the overall ORR is 39%. The data from at least 23 patients are required to obtain results. Seven patients will be enrolled in stage 1. When the number of valid patients ≤ 1 , combination therapy will be considered not superior to monotherapy, and this trial will be terminated. Otherwise, 16 subjects will be enrolled in stage 2. The trial is rejected if the total number of patients with ORR in the two stages is ≤ 5 .

The intention-to-treat principle will be adopted in the efficacy analysis, and all enrolled subjects will be included. Frequency and percentage will be used for categorical data, and the χ^2 test or exact probability will be used for intergroup comparison. Mean and standard deviation (or median and interquartile range) will be used for quantitative data. The t-test or a non-parametric test will be used for intergroup comparison, the K-M method for survival estimation, and the log-rank test for intergroup comparison.

4. Trial Population

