- Blood routine/blood biochemistry/urine routine/stool routine (within 3 days before the 1st dose);
- Coagulation function tests (within 3 days before the 1st dose);
- Pregnancy test;
- Thyroid function test;
- HIV antibodies, Hepatitis B-five test (HBsAg, HBsAb, HBcAb, HBeAg, HBeAb) and HBV-DNA (if the subject is positive for HBsAg and HBeAg), HCV antibody and HCV-RNA (if the subject is positive for HCV antibody);
- Evaluation of adverse events;
- Radiologic tumor evaluation;
- Pathology consultation
- Archived or fresh tumor tissue samples (non-essential).

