10.2. Proposed test items

- [name] laboratory will contact relevant sequencing companies for whole-exome sequencing of tumor tissues
- [name] laboratory will perform immunohistochemistry and immunofluorescence (including but not limited to PD-1, PD-L1, and lymphocyte molecular markers such as CD4, CD8) on tumor tissues
- [name] laboratory will carry out methylation tests of tumor tissues

- [name] laboratory will perform ELISA, plasma free nucleotide test, and flow cytometry of patients' blood samples.

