11.2. Statistical analysis plan

Baseline data will be analyzed based on the FAS. Full analysis set (defined as all included patients) and safety analysis set (defined as patients had at least one cycle of treatment) were used for efficacy analysis and safety analysis, respectively. In general, categorical data will be summarized using number of patients (n), frequency and percentages. Two-sided exact 95% confidence intervals (CIs) based on the Clopper-Pearson method will be provided to summarize the binomial proportion of the ORR and DCR for both RECISTv1.1 and irRECIST assessments where applicable. Continuous data will be summarized using the number of patients, mean, standard deviation, median, first and third quartiles (Q1, Q3), minimum, and maximum. Time-to-event analyses will be performed using Kaplan-Meier (KM) methods. Medians of PFS and DOR were analyzed using the Kaplan-Meier curve, and 95% CIs were calculated with a generalized Brookmeyer and Crowley method. We calculated the probabilities of patients achieving a PFS > 6 months or > 12 months using the Kaplan-Meier product-limit method, and reverse Kaplan-Meier calculated the Greenwood Formula Follow-up time. Cox regression models were used to test the association between clinicopathologic and genetic characteristics and PFS, and a P-value < 0.05 was considered significant. For genomic analysis, P-value < 0.1 was considered statistically significant. All statistical analyses

about clinical listings will be performed using SAS v9.4 or higher. Gene analysis will be performed using R V4.1.0 or higher

12. Ethical Standards

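### Genomic results are called statistically significant at P < 0.1 with no stated multiplicity control, next to a conflicting P < 0.05 rule for genetic associations with PFS

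*Protocol*

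**What the plan says.** Two adjacent sentences in protocol section 11.2 set thresholds that cover genetic data.

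- On PFS: "Cox regression models were used to test the association between clinicopathologic and genetic characteristics and PFS, and a P-value < 0.05 was considered significant".
- On genomics: "For genomic analysis, P-value < 0.1 was considered statistically significant".

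Neither mentions adjustment for multiple tests, a candidate gene list or a number of tests. Section 11.2 does not say whether the second sentence replaces the first for genetic markers.

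Section 10.2 shows how wide the testing may be. The laboratory "will contact relevant sequencing companies for whole-exome sequencing of tumor tissues", and the "laboratory will carry out methylation tests of tumor tissues".

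On the sample, section 3.1 says: "The data from at least 23 patients are required to obtain results" (7 in stage 1 and 16 in stage 2). The screening list in section 8.1 marks tumour tissue as non-essential, so fewer patients than are enrolled may be sequenced.

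On status, section 2.3 lists the aim as exploratory: "To explore molecular biology markers that can predict efficacy". The closing paragraph of section 1.6 likewise speaks of an exploratory look at prognostic factors.

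**The concern.** The threshold is loosened where the number of tests is likely to be largest. A per-test limit of 0.1 does not bound the number of chance findings, which grows in proportion to the number of tests, and an exome screen can involve very many.

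The two sentences also overlap. A gene tested against PFS is a genetic characteristic in a Cox model and is also part of a genomic analysis. Whether it counts as significant between P = 0.05 and P = 0.1 depends on which sentence the analyst applies, and that choice could be made after the data are seen.

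At stake is how the marker results are read. Under the rule as written, chance associations would be reported as statistically significant under an aim worded as prediction of efficacy. In a single arm every patient receives the combination, so a marker of treatment benefit cannot be told from a marker of good prognosis.

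**Working it through.** **Inputs from the protocol.** Genomic threshold 0.1; threshold for Cox models of PFS 0.05 (both section 11.2); planned N = 7 + 16 = 23, with ORR 13% against 39%, one-sided alpha 0.05 and power 0.80 (section 3.1).

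**Assumptions, because the protocol gives no figures.** Number of tests m; share π of tested markers that are real; power per marker; for one illustration, 18 PFS events, 30% marker prevalence and a hazard ratio of 0.5.

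**Step 1: the sample size.** Stopping at 1 or fewer responses in 7 and rejecting the treatment at 5 or fewer in 23 gives, by exact binomial calculation, alpha 0.0456 and power 0.8003. So N = 23 reproduces. It was chosen for the ORR test, not for marker work.

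**Step 2: the two rules on one result.** For a gene-PFS association at P = 0.07: 0.07 > 0.05, not significant under the Cox sentence; 0.07 < 0.1, significant under the genomic sentence. The rules disagree for every P from 0.05 up to 0.1.

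**Step 3: chance findings when no marker is real.** Expected false positives = 0.1m; probability of at least one = 1 − 0.9^m, for independent tests that attain nominal size.

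| m | expected | P(at least one) at 0.1 | P(at least one) at 0.05 |
|---|---|---|---|
| 10 | 1 | 65% | 40% |
| 20 | 2 | 88% | 64% |
| 50 | 5 | 99.5% | 92% |
| 100 | 10 | >99.9% | 99.4% |

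The last column uses 1 − 0.95^m. Settling the clash in favour of 0.05 would therefore not be enough.

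**Step 4: share of declared markers that are false.** Step 3 cannot give this, because with no real markers every declaration is false by construction. With real markers, share false = 0.1(1 − π) / [0.1(1 − π) + power × π].

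- π = 5%, power 80%: 0.095 / (0.095 + 0.040) = 70.4%.
- π = 5%, power 20%: 0.095 / (0.095 + 0.010) = 90.5%.
- π = 10%, power 80% to 20%: 52.9% to 81.8%.
- π = 20%, power 50%: 0.080 / (0.080 + 0.100) = 44.4%.
- π = 20%, power 80%: 0.080 / (0.080 + 0.160) = 33.3%.

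More than half are false when π < 0.1 / (0.1 + power), that is, below 11% at power 80%, 17% at 50% and 33% at 20%.

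**Step 5: plausible power.** By the Schoenfeld approximation, √(18 × 0.3 × 0.7) × ln 2 = 1.348. At two-sided 0.1, power = Φ(1.348 − 1.645) = 38%.

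**Step 6: does the nominal 0.1 hold in small samples?** Suppose 9 of 23 respond (39%, the design alternative). The smallest two-sided Fisher P for a gene altered in one patient is 9/23 = 0.39. For two patients it is (9 × 8)/(23 × 22) = 0.14. Such genes can never reach 0.1. For genes altered in 3 to 12 patients the actual size is 1% to 9%. Exact tests of response thus give fewer false positives than 0.1m. The log-rank test of PFS does not share this protection: simulated with 23 patients, 18 events and 3 to 10 carriers, it rejected a true null 11% to 14% of the time.

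**The case against.** The strongest reply is that the analysis is openly exploratory. Sections 1.6 and 2.3 say so, and no primary or secondary endpoint, stopping rule or enrolment decision uses these P-values. A liberal threshold is defensible when screening for leads. A separate SAP may add false-discovery control, and gene filters or methods for sparse data properly belong there. All of this stands and lowers the weight. It does not remove the point: the protocol itself fixes a rule, attaches the words statistically significant to it, and sets it beside a different threshold for overlapping analyses. A SAP would have to override that text.

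A reader might also infer more than the documents support:

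- **That most declared markers will be false.** This depends on the number of tests and the share of real markers, neither of which is stated. Step 4 shows shares below half for a short, well-supported list.
- **That 0.1 governs every biomarker assay.** The rule names genomic analysis. Nothing applies it to the immunohistochemistry, ELISA or flow cytometry listed in section 10.2.
- **That at most 23 patients contribute.** The protocol says at least 23. A smaller sequenced number is possible because tissue is optional, but none is given.
- **That the trial's main conclusion, or the later selection of patients, is compromised.** The ORR test does not use this rule, and no section says the markers will select patients.

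**Conclusion.** The point holds as a defect in a stated rule, with modest weight. Two parts need no assumption: section 11.2 calls genomic results significant at 0.1 with no multiplicity control stated, and it gives genetic associations with PFS two different thresholds. The size of the first part does rest on assumptions. For independent null tests at nominal size, 20 tests carry an 88% chance of at least one false declaration and 100 tests make one almost certain; exact tests on rarely altered genes would give fewer. With 5% real markers, about 70% to 90% of declarations would be false. The false share falls below half once roughly 11% to 33% of tested markers are real, depending on power. The primary analysis is untouched.

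**What to change.** In section 11.2, delete the P < 0.1 sentence and take genetic characteristics out of the P < 0.05 sentence, so that genomic associations have one rule. State that rule as Benjamini-Hochberg q-values at a 10% false discovery rate, applied separately within the exome and methylation families, with effect estimates and 95% CIs. This keeps the sponsor's 10% tolerance but applies it to the markers declared. If no marker is real and tests are independent, the chance of any false declaration in a family is then 10%, against 88% at m = 20 under the present rule.

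Describe the results, here and under the section 2.3 aim, as hypothesis-generating associations rather than predictors of treatment effect.

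The cost is wording only: no added patients, samples or assays. The price is fewer declared markers. A lone marker would need P ≤ 0.1/20 = 0.005 among 20 tests. In the Step 5 illustration, power at that limit is Φ(1.348 − 2.807) = 7%, against 38% at 0.1. That is why the estimates and intervals, not the significance label, should carry the report.

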12.1. Informed consent

The study physician is responsible for a complete and comprehensive introduction of the study objectives, drug performance, possible toxic side effects, and potential risks, patients' rights, items to be complied with, and risk and benefits to the patient or his/her proxy before the subject is enrolled. Patients must sign the informed consent form before enrollment, and the signed form will be retained in the CRF.

12.2. Subjects' benefits

The investigational drugs used in this study are free of charge. Relevant insurance will be purchased for the patients in this study at around 250 RMB/person. The maximum compensation is around 30,000/person. The insurance will guarantee the subjects' safety.

12.3. Subject compensation

Compensation claims arising from the investigational drug should be settled in accordance with the related clinical trial regulations of the hospital and the Chinese government.

12.4. Ethical standards, laws, and regulations

The clinical trial must comply with the "2004 Declaration of Helsinki," "Good Clinical Practice (GCP)" released by the NMPA, and pertinent laws and regulations. The ethics committee of the leading site must approve this protocol before the study can be initiated. Any revisions to the study protocol during the study must be reported to the ethics committee and filed.

13. Study Management

13.1 Case report form

The primary objective is to obtain the data required by the study protocol in a complete, accurate, clear, and prompt manner. Data in the case report form should be identical to the source documents.

The case report form must be filled completely and clearly (use a black or blue ballpoint pen to comply with legal document requirements). All revisions and corrections must be performed and confirmed by the investigator, and the date of revision/correction must be stated. Errors must be clearly retained and not covered by corrected data (such as the use of correction fluid). The investigator must state his/her reason for revising important data.

For information/notes missing in the medical record, lines should be drawn in the empty spaces in the case report form to avoid subsequent unnecessary investigations.

The case report form is a regulatory document that must be submitted to the hospital authorities.

Appendix 1. ECOG Scale of Performance Status (ECOG PS).

Activity score	Description
0	Asymptomatic, fully active, able to carry on all pre-disease activities without restriction.
1	Symptomatic, restricted in physically strenuous activity but ambulatory, and able to carry out work of a light or sedentary nature, such as light housework and office work.
2	Symptomatic, ambulatory, and capable of self-care but unable to carry out any work activities, up and about >50% of waking hours.
3	Symptomatic, capable of only limited self-care, confined to bed or chair more than 50% of waking hours, but is not bedridden.
4	Completely disabled, cannot carry on any self-care, bedridden.
5	Dead.
